3.0 STUDY DESIGN

- This will be a phase II, single-arm, open-label, non-randomized study with a safety lead-in phase.
- Patients will receive 5-azacytidine subcutaneously or intravenously daily for the first 7 days of each treatment cycle. For the lead-in portion, the length of the cycle will be at least 28 days to evaluate DLT. Subsequently cycles will be repeated approximately every 28 days (+/-7 days), and therapy will be continued until clinically significant disease progression or documentation of unacceptable toxicity.
- Patients will receive therapy with lirilumab IV infusion on Day 8 (+/-2 days) of each 5-azacytidine cycle.
- The historical experience in relapsed/refractory AML patient population is that response with single agent hypomethylator therapy (5-azacytidine or decitabine), when available, is 10-15%. In many instances (eg, patients with relapsed/refractory AML beyond first salvage) no standard therapy is available. Thus, an overall response rate of 30% will be considered significant.

4.0 PATIENT SELECTION

Patients must have baseline evaluations performed prior to the first dose of study drug and must meet all inclusion and exclusion criteria. Results of all baseline evaluations, which assure that all inclusion and exclusion criteria have been satisfied, must be reviewed by the Principal Investigator or his/her designee prior to enrollment of that patient. In addition, the patient must be thoroughly informed about all aspects of the study, including the study visit schedule and required evaluations and all regulatory requirements for informed consent. The written informed consent must be obtained from the patient prior to initiating treatment or any study-specific procedures. The following criteria apply to all patients enrolled onto the study unless otherwise specified.

4.1 Inclusion Criteria

- 4.1.1 Patients with AML or biphenotypic or bilineage leukemia who have failed at least one prior therapy. Patients with AML should have failed prior therapy

or have relapsed after prior therapy.

- 4.1.2 Patients should not be eligible or able to receive approved therapy of confirmed clinical benefit in this patient population
- 4.1.3 Patients with MDS or CMML who received therapy for the MDS or CMML and progress to AML are eligible at the time of diagnosis of AML regardless any prior therapy for AML. The WHO classification will be used for AML.
- 4.1.4 Prior therapy with hydroxyurea, chemotherapy, biological or targeted therapy (e.g. FLT3 inhibitors, other kinase inhibitors), or hematopoietic growth factors is allowed.
- 4.1.5 Age ≥ 18 years.
- 4.1.6 Eastern Cooperative Oncology Group (ECOG) Performance Status ≤ 2 .
- 4.1.7 Adequate organ function: total bilirubin ≤ 2 times upper limit of normal (\times ULN) ($\leq 3 \times$ ULN if considered to be due to leukemic involvement or Gilbert's syndrome); aspartate aminotransferase or alanine aminotransferase $\leq 2.5 \times$ ULN ($\leq 5.0 \times$ ULN if considered to be due to leukemic involvement); serum creatinine $\leq 2 \times$ ULN or GFR ≥ 50
- 4.1.8 Patients must provide written informed consent
- 4.1.9 In the absence of rapidly progressing disease, the interval from prior treatment to time of initiation of 5-azacytidine and lirilumab will be at least 2 weeks OR at least 5 half-lives for cytotoxic/noncytotoxic agents. Use of one dose of cytarabine (up to 2 g/m²) is allowed prior to the start of study therapy or hydroxyurea for patients with rapidly proliferative disease is allowed before the start of study therapy and while the patient is on active study treatment, as needed, for clinical benefit and after discussion with the PI. Concurrent therapy for CNS prophylaxis or continuation of therapy for controlled CNS disease is permitted
- 4.1.10 Females must be surgically or biologically sterile or postmenopausal (amenorrheic for at least 12 months) or if of childbearing potential, must have a negative serum or urine pregnancy test within 72 hours before the start of the treatment
- 4.1.11 Women of childbearing potential must agree to use an adequate method of contraception during the study and until 3 months after the last treatment. Males must be surgically or biologically sterile or agree to use an adequate method of contraception during the study until 3 months after the last treatment.

Adequate methods of contraception include:

- Total abstinence when this is in line with the preferred and usual lifestyle of the patient. Periodic abstinence (e.g., calendar, ovulation, symptothermal, post-ovulation methods) and withdrawal are not acceptable methods of contraception.
- Female sterilization (have had surgical bilateral oophorectomy with or without hysterectomy) or tubal ligation at least six weeks before taking study treatment. In case of oophorectomy alone, only when the reproductive status of the woman has been confirmed by follow up hormone level assessment
- Male sterilization (at least 6 months prior to screening). For female patients on the study, the vasectomized male partner should be the sole partner for that patient
- Combination of any of the two following (a+b or a+c or b+c)
 - a. Use of oral, injected or implanted hormonal methods of contraception or other forms of hormonal contraception that have comparable efficacy (failure rate <1%), for example hormone vaginal ring or transdermal hormone contraception
 - b. Placement of an intrauterine device (IUD) or intrauterine system (IUS)
 - c. Barrier methods of contraception: Condom or Occlusive cap (diaphragm or cervical/vault caps) with spermicidal foam/gel/film/cream/vaginal suppository

In case of use of oral contraception, women should have been stable on the same pill before taking study treatment.

Note: Oral contraceptives are allowed but should be used in conjunction with a barrier method of contraception due to unknown effect of drug-drug interaction.

Women are considered post-menopausal and not of child bearing potential if they have had 12 months of natural (spontaneous) amenorrhea with an appropriate clinical profile (e.g. age appropriate, history of vasomotor symptoms) or have had surgical bilateral oophorectomy (with or without hysterectomy) or tubal ligation at least six weeks ago. In the case of oophorectomy alone, only when the reproductive status of the woman has been confirmed by follow up hormone level assessment is she considered not of child bearing potential.

4.2 Exclusion Criteria

- 4.2.1 Patients with known allergy or hypersensitivity to lirilumab, 5-azacytidine, or any of their components. Patients who have previously been treated with lirilumab in combination with 5-azacytidine will be excluded.
- 4.2.4 Patients with a known history of severe interstitial lung disease or severe pneumonitis or active pneumonitis that is uncontrolled in the opinion of the

treating physician.

- 4.2.5 Patients with a known history of any of the following autoimmune diseases are excluded: (a) patients with a history of inflammatory bowel disease (including Crohn's disease and ulcerative colitis) (b) patients with a history of rheumatoid arthritis, systemic progressive sclerosis [scleroderma], Systemic Lupus Erythematosus, autoimmune vasculitis [e.g., Wegener's Granulomatosis]).
- 4.2.6 Patients with organ allografts (such as renal transplant) are excluded
- 4.2.7 Patients with allogeneic stem cell transplantation within the last 6 months or patients with active GVHD will be excluded
- 4.2.8 Ongoing immunosuppressive therapy, including cyclosporine and tacrolimus. Patients who are on high dose steroid. Note: Subjects may be using systemic corticosteroids (daily doses ≤ 10 mg of prednisone or equivalent) or topical or inhaled corticosteroids.
- 4.2.9 Patients with symptomatic CNS leukemia or patients with poorly controlled CNS leukemia.
- 4.2.10 Active and uncontrolled disease/ (active uncontrolled infection, uncontrolled hypertension despite adequate medical therapy, active and uncontrolled congestive heart failure NYHA class III/IV, clinically significant and uncontrolled arrhythmia) as judged by the treating physician.
- 4.2.11 Patients with active and uncontrolled Human Immunodeficiency Virus (HIV) infection will be excluded. However, patients with well controlled HIV infection will be considered.
- 4.2.12 Patients known to be positive for hepatitis B by surface antigen expression. Patients known to have active hepatitis C infection (positive by polymerase chain reaction or on antiviral therapy for hepatitis C within the last 6 months)
- 4.2.13 Any other medical, psychological, or social condition that may interfere with study participation or compliance, or compromise patient safety in the opinion of the investigator
- 4.2.14 Patients unwilling or unable to comply with the protocol.
- 4.2.15 Pregnant or breastfeeding
- 4.2.16 Acute promyelocytic leukemia (APL).

5 TREATMENT PLAN

5.1 General

All patients will be registered through CORE. The objective will be to administer lirilumab and 5-azacytidine at full dose. We will first treat 6 patients at dose level -1. Other dose levels will be used for dose adjustments for toxicity during therapy.

5.2 Schedule

The Investigator is responsible for completing the cohort summary template and submitting to the IND office Medical Monitor for review and approval prior to advancing subjects to the next protocol specified cohort/dose level. A copy of the cohort summary should be placed in the Investigator's Regulatory Binder under "sponsor correspondence". This should be submitted after the first six patients.

5.2.1 Patients will be treated according to the following schedule:

- 5-azacytidine will be administered subcutaneously (SQ) or intravenously (IV) for 7 days of every cycle (Days 1-7) as determined by treating physician. Both SQ and IV forms of administration are FDA approved and considered interchangeable. Patients may start receiving 5-azacytidine by one route and changed to the other at any time as needed based on patient and/or physician preference.
- Lirilumab will be administered as an approximately 60 minute IV infusion on Day 8 (+/-2 days) of each 5-azacytidine cycle. Lirilumab will be administered every cycle with no interruptions unless there are adverse events as described in Section 5.3. The dosing calculations should be based on the body weight. All doses should be rounded to the nearest milligram. There will be no dose reductions (only interruptions when indicated) allowed for lirilumab on this trial.
- 5-azacytidine at a dose of 75 mg/m² on days 1-7 has been shown to be safe in combination with multiple agents including lenalidomide[49], bortezomib[49], and vorinostat[50, 51]. IPH2101 is the first fully-human anti-KIR monoclonal antibody, and lirilumab is the second generation. Both products bind to the same KIR subtypes with similar affinities. Functionally and biologically, the 2 antibodies are similar with the following exceptions: 1) IPH2101 is a non-recombinant protein that is produced by a murine hybridoma cell line; whereas, lirilumab is a recombinant product produced in CHO cells. 2) Lirilumab has a single amino acid substitution of a serine to a proline in the IgG4 heavy chain, resulting in greater stability of the compound by reducing the formation of half antibodies. IPH2101 studies were done prior to lirilumab studies and safety, efficacy, PKs, and immunologic correlates of IPH2101 in a phase 1 trial in elderly AML in first remission have been published (Vey N, et al., Blood, 2012 Nov 22;120(22):4317-23). Patients received escalating doses (0.0003-3 mg/kg) of IPH2101 following a 3 + 3 design. The doses that elicited full occupancy

were: 1 week = 0.075 mg/kg, 2 weeks = 1 mg/kg, and for at least 4 weeks = 3 mg/kg. There was a clear correlation between mAb exposure and KIR occupancy. The maximum tolerated dose was not reached, although full KIR saturation (> 90%) was sustained for 4 weeks only at the 3 mg/kg. Lirilumab dose of 3 mg/kg every 4 weeks is also the highest dose to be tested in BMS study of lirilumab in combination with elotuzumab for multiple myeloma: *A Phase I Open Label Dose Escalation and Randomized Cohort Expansion Study of the Safety and Tolerability of Elotuzumab (BMS-901608) Administered in Combination With Either Lirilumab (BMS-986015) or Urelumab (BMS-663513) in Subjects With Multiple Myeloma*” (study identifier: NCT02252263). Based on this data and the tolerability of lirilumab in combination with other agent (namely nivolumab) in the CA223001 the maximum dose for this trial of lirilumab 3.0 mg/kg every 4 weeks is the recommended phase 2 dose (RP2D) from ongoing Phase 2 study (IPH2102-101). We propose the starting dose level of 5-azacytidine 75 mg/m² x 7 days and lirilumab 1.0 mg/kg on day 8 of each 28 (+/- 7) day cycle to be escalated or de-escalated based on occurrence of DLTs as described below. The lead-in phase is to ensure that the combination is well tolerated with no unexpected side effects.

5.2.1.1 The starting dose will be dose level -1.

Table 1. Dose levels of 5-azacytidine and lirilumab during the lead-in phase (part a)

Dose level	5-azacytidine (mg/m ² /d, Days 1-7)	Lirilumab (mg/kg, day 8)
-4	25	0.3
-3	50	0.3
-2	75	0.3
-1	75	1.0 (Starting dose)
0	75	3.0

5.2.1.2 The goal of the lead-in phase is to identify the dose at which <2/6 patients experience DLT. During the lead-in phase the dose’s of 5-azacytidine and lirilumab may be reduced if 2 or more patients experience DLT at any given dose. After the lead in phase the dose of lirilumab may not be reduced in the phase II portion of the study. For potential lirilumab related AEs in the phase II portion of the study only dose interruptions of lirilumab will be permitted. Dose reductions or escalations of 5-azacytidine will continue to be permitted in the phase II portion of the study and dose reductions or escalations of 5-azacytidine beyond those mentioned in table 5 or different to the doses specified should be discussed with the PI and documentation of the justification recorded in the chart.

5.2.1.3 The dose and /or schedule of administration is subject to modification pending information from ongoing clinical trials of lirilumab as a single agent and in combination with other drugs.

DLT is defined as clinically significant non-hematologic adverse event or abnormal laboratory value assessed as unrelated to disease progression, intercurrent illness, or concomitant medications and occurring during the first cycle on study that meets any of the following criteria:

- CTCAE Grade 3 AST (SGOT) or ALT (SGPT) for ≥ 7 days
- CTCAE Grade 4 AST (SGOT) or ALT (SGPT) of any duration
- All other clinically significant non-hematological adverse event that is Grade 3 or 4 according to the NCI common terminology criteria version 4.0 with the following exceptions:
 - Grade 3 or 4 nausea, vomiting and diarrhea will be considered DLT only if not controlled by optimal therapy.
 - Grade 3 biochemical abnormalities (e.g., lipase or bilirubin elevation) will only be considered DLT if accompanied by clinical consequences. Grade 3 or 4 electrolyte abnormalities will only be considered DLT if possibly related to study drug and not corrected by optimal replacement therapy.

5.2.1.4 We will first treat 6 patients at dose level -1 in the lead-in phase. If DLT occurs in $\geq 2/6$ patients, this dose level would exceed the MTD, and 6 patients will be treated at the next lower dose level (i.e. dose level -2). If DLT is observed in the first 28 days of treatment in 0 or 1/6 at dose level -1, then dose level 0 will be evaluated. The dose adjustment (Table 1) will continue in cohorts of 6 until we reach a dose level at which $< 2/6$ patients experience a DLT in the first 28 days. The dose level at which 0-1/6 patients experience a DLT in the first 28 days of treatment will be the MTD and will be used to treat an additional 34 patients in the phase II portion of the study. If $\geq 2/6$ patients experience DLT at dose level -4, the study will be revised to consider additional lower dose levels (based on potential synergistic toxicity).

5.2.1.5 Patients that are removed from study before day 28 for any reason other than toxicity and have not experienced DLT will be replaced.

5.2.2 One cycle of therapy is defined as 28 days. Patients will receive one cycle of therapy every 28 days (+/- 7 days).

5.2.2.1 In the phase II part of the study (once the MTD dose has been defined) cycles may be started early (but not earlier than day 21) for patients with active disease if judged in the best interest of the patient.

For the lead-in cohort, DLT defining period is 28 days. As such, cycle 2 should not be started before 28 days for the patients being treated on the lead-in cohort.

5.2.2.2 Subsequent cycles may be delayed for recovery of toxicity or other medical conditions (e.g. infections). Delays in start of subsequent cycles greater than 8 weeks will be acceptable only for patients who are deriving clinical benefit and after discussion with the principal investigator of potential risk/benefit ratio.

5.2.2.3 In instances where one drug has to be discontinued transiently because of safety, the administration of the other drug may continue as scheduled. If the drug that is held can resume at a later time, no doses will be made up and the administration will follow the originally defined schedule calendar according to the drug that was continued.

5.2.2.4 Subsequent courses of 5-azacytidine and lirilumab may be administered regardless of peripheral blood counts during the first 4 cycles and/or in the presence of residual leukemia.

If prolonged myelosuppression (more than 8 weeks) WITH evidence of a hypocellular marrow (marrow cellularity less than 5% without evidence of leukemia) is observed, 5-azacytidine and lirilumab will be discontinued. Delays in start of subsequent cycles greater than 8 weeks will be acceptable only for patients who are deriving clinical benefit and after discussion with the principal investigator of potential risk/benefit ratio. If the peripheral counts do not recover (ANC $<1 \times 10^9/L$ and/or platelets $<30 \times 10^9/L$) but there is evidence of residual leukemia in the bone marrow, subsequent cycles can be administered at the discretion of the treating physician not earlier than 21 days after the prior cycle.

5.2.2.4 For patients who discontinue therapy, the reason for treatment discontinuation will be captured.

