Blockade of inhibitory KIR by lirilumab is thus a promising mechanism to promote killing of tumor cells by the innate immune system. IPH2101 is the first fully-human anti-KIR monoclonal antibody, and lirilumab is the second generation. Both products bind to the same KIR subtypes with similar affinities. Functionally and biologically, the 2 antibodies are similar with the following exceptions: 1) IPH2101 is a non-recombinant protein that is produced by a murine hybridoma cell line; whereas, lirilumab is a recombinant product produced in CHO cells. 2) Lirilumab has a single amino acid substitution of a serine to a proline in the IgG4 heavy chain, resulting in greater stability of the compound by reducing the formation of half antibodies. IPH2101 studies were done prior to lirilumab studies and safety, efficacy, PKs, and immunologic correlates of IPH2101 in a phase 1 trial in elderly AML in first remission have been published (Vey N, et al., Blood, 2012 Nov 22;120(22):4317-23). Patients received escalating doses (0.0003-3 mg/kg) of IPH2101 following a 3 + 3 design. The doses that elicited full occupancy were: 1 week = 0.075 mg/kg, 2 weeks = 1 mg/kg, and for at least 4 weeks = 3 mg/kg. There was a clear correlation between mAb exposure and KIR occupancy. The maximum tolerated dose was not reached, although full KIR saturation (> 90%) was sustained for 4 weeks only at the 3 mg/kg. Lirilumab dose of 3 mg/kg every 4 weeks is also the highest dose to be tested in BMS study of lirilumab in combination with elotuzumab for multiple myeloma: *A Phase I Open Label Dose Escalation and Randomized Cohort Expansion Study of the Safety and Tolerability of Elotuzumab (BMS-901608) Administered in Combination With Either Lirilumab (BMS-986015) or Urelumab (BMS-663513) in Subjects With Multiple Myeloma* (study identifier: NCT02252263). Based on this data and the tolerability of lirilumab in combination with other agent (namely nivolumab) in the CA223001 trial we would like to evaluate escalating doses of lirilumab to a maximum potential dose of 3.0 mg/kg every 4 weeks in this study.

For details of lirilumab preclinical studies, clinical studies, toxicities, pharmacokinetics, and adverse events please see the most recent version of the Lirilumab Investigator Brochure (Appendix E).

2.5 5-azacytidine (Vidaza):

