- Bone marrow samples will be collected under an IRB-approved laboratory protocol for testing of biomarkers at baseline, at day 28 (+/-7 days), then every 1-3 cycles, and at progression whenever possible.

All these samples can be obtained +/- 3 days. Missed samples for correlative studies will not constitute protocol deviations. All correlative samples are optional.

- 7.2.8 For patients that remain on study with no significant toxicity for more than 6 months, subsequent evaluations during study may be modified after discussion with the principal investigator. These include a decrease in frequency of bone marrow aspirations to every 6-12 months (or as clinically indicated), correlative studies to every 6-12 months (or suspension of sample collection for correlative studies), other laboratory tests to once every cycle.
- 7.2.9 ALL treatments with lirilumab must be administered at the MDACC outpatient clinic. The first cycles of azacytidine must be administered at the MDACC outpatient clinic. Subsequently, patients will have the option of receiving 5-azacytidine injections or infusions at the MDACC outpatient clinic or local ambulatory treatment center. If the local treatment center cannot accommodate 7 consecutive day administration on Days 1-7 of 5-azacytidine, it is allowable to be administered on a 5+2 (days off) + 2 schedule (For example, Administer Monday through Friday, omit Saturday and Sunday, Resume/Administer Monday and Tuesday). In the event that the 5+2+2 schedule is utilized, the Lirilumab will be administered on Day 10, which is allowable by schedule window or +/- 2 days from Day 8. We do not intend for the subjects to receive lirilumab at an outside physician's office. During the first cycle all the laboratory evaluations will be done at MDACC. Subsequently, the patient may have the laboratory work done at a local clinic and the results reported to the research nurse for the study. The laboratory work done at the local clinic will be forwarded to the patient's attending physician at MDACC or PI of the study, who will sign off on the labs to verify that the results have been reviewed.

Outside Physician Participation During Treatment

1. MDACC Physician communication with the outside physician is required prior to the patient returning to the local physician.
This will be documented in the patient record

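### The stated lirilumab maximum of 3.0 mg/kg every 4 weeks is not held by the plan's own cycle and visit windows, which permit doses about 3 weeks apart in phase II

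*Combined protocol and SAP*

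**What the plan says.** The ceiling appears twice. Section 2.4 proposes "escalating doses of lirilumab to a maximum potential dose of 3.0 mg/kg every 4 weeks in this study". The dose rationale in Section 5.2.1 says "the maximum dose for this trial of lirilumab 3.0 mg/kg every 4 weeks is the recommended phase 2 dose (RP2D".

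The timing rules are these:

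- Section 5.2.1: "Lirilumab will be administered as an approximately 60 minute IV infusion on Day 8 (+/-2 days) of each 5-azacytidine cycle". The same item has lirilumab given in every cycle unless adverse events intervene. Section 5.3.3 ties the next lirilumab dose to the projected day 8 of the next cycle.
- Section 5.2.2: "Patients will receive one cycle of therapy every 28 days (+/- 7 days"; Section 3.0 and the dose rationale in 5.2.1 give the same window.
- Section 5.2.2.1, for phase II: "cycles may be started early (but not earlier than day 21) for patients with active disease", if judged to be in the patient's best interest.
- Section 5.2.2.4: with residual leukemia and unrecovered counts, the next cycle may follow from 21 days after the prior one.
- Section 5.2.2.1, for the lead-in: "cycle 2 should not be started before 28 days for the patients being treated on the lead-in cohort".
- Section 7.2.9: when 5-azacytidine is given on the 5+2+2 schedule, "the Lirilumab will be administered on Day 10, which is allowable by schedule window or +/- 2 days from Day 8".

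Section 5.2.1.4 takes the dose level with 0-1 DLTs among 6 patients in the first 28 days as the MTD and gives it to 34 more patients. Section 5.2.1.2 then rules out lirilumab dose reductions in phase II and allows only interruptions.

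**The concern.** The maximum is worded as milligrams per kilogram together with an interval, but only the milligrams per kilogram are controlled. The interval depends on when the next 5-azacytidine cycle starts and on the visit window, and both can shorten it well below 4 weeks. A site that follows every scheduling rule could therefore give lirilumab more often than the plan's stated maximum, and nothing in the visible text would flag it.

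Two things are at stake. The first is safety: the dose rationale in Sections 2.4 and 5.2.1 rests mainly on 4-weekly experience, namely receptor occupancy sustained for 4 weeks at 3 mg/kg with the predecessor antibody and 3 mg/kg every 4 weeks with nivolumab. The second is interpretation: the phase II toxicity and response rates would pool patients on roughly 3-weekly and roughly 4-weekly lirilumab under one dose label.

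**Working it through.** **Inputs.** Lirilumab day d is 6 to 10 (day 8 ± 2, Section 5.2.1). L is the number of days from day 1 of one cycle to day 1 of the next. L = 28 is nominal; L = 21 and L = 35 are the ends of the ± 7 window (Section 5.2.2). L = 20 applies if the next cycle's day 1 is day 21 itself (Section 5.2.2.1). The wording in 5.2.2.4, counting 21 days after the prior cycle, gives L = 21. For lead-in cycle 2, L is 27 or 28, depending on whether day 28 may itself be the new day 1.

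**Formula.** Interval between lirilumab doses = L + d(next) − d(previous).

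**The plan's own figure.** L = 28 with day 8 both times: 28 + 8 − 8 = 28 days, which reproduces every 4 weeks.

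**What the windows permit (days between doses).**

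| Case | L | Day 8 to day 8 | Shortest (day 10, then day 6) | Longest (day 6, then day 10) |
|---|---|---|---|---|
| Nominal | 28 | 28 | 24 | 32 |
| 21-day cycle | 21 | 21 | 17 | 25 |
| Next cycle starts on day 21 | 20 | 20 | 16 | 24 |
| Lead-in cycle 2, started on day 28 | 27 | 27 | 23 | 31 |
| 35-day cycle | 35 | 35 | 31 | 39 |

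The 16 and 17 day intervals cannot repeat back to back. After a day-6 dose, the next interval in a 21-day cycle is at least 21 + 6 − 6 = 21 days (20 if L = 20). Sustained short spacing is therefore 20-21 days.

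**Dose intensity at 3.0 mg/kg (dose level 0).**

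- Stated maximum: 3.0 / 4 weeks = 0.75 mg/kg/week.
- Sustained 21-day cycles: 3.0 / 3 weeks = 1.00 mg/kg/week; 28/21 = 1.33 times the maximum.
- Sustained 20-day spacing: 28/20 = 1.40 times.
- Isolated 17-day interval: 28/17 = 1.65 times, or 4.94 mg/kg per 28 days.
- Isolated 16-day interval: 28/16 = 1.75 times, or 5.25 mg/kg per 28 days.

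**At 1.0 mg/kg (dose level -1).** Even a 16-day interval gives 1.0 × 28/16 = 1.75 mg/kg per 28 days, below 3.0. The stated maximum is not exceeded at this level or below.

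**What the lead-in observes.** The first lirilumab dose falls on study day 6-10. In the lead-in, cycle 2 starts on study day 28 or 29 at the earliest, so its day 6 is study day 33 or 34, after the 28-day DLT period. One dose falls inside the period and no repeat-dose interval is assessed. In phase II, cycle 2 may start on study day 21 or 22, so a second dose may fall on study day 26 or 27, within the first 28 days.

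**The case against.** The best defence is that every 4 weeks is only the nominal name of the schedule. The sentence after the quoted one in Section 5.2.1 openly gives the cycle as 28 days with a 7-day window. Table 1 defines dose levels by mg/kg on day 8 with no interval, and Section 5.3.6 makes the ceiling operational as dose level 0. This has weight: no section defines a limit in mg/kg/week. But two sections attach the interval to the word maximum, and the scheduling rules then allow a shorter one, so the texts still need reconciling.

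Several stronger readings are tempting, and the documents do not support them:

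- *The lead-in validates 4-weekly dosing and phase II departs from it.* The DLT period holds a single lirilumab dose, so it leaves a 28-day and a 21-day interval equally unassessed. What stands is narrower: the MTD assesses no repeat interval, and lead-in cycle 2 is held to at least 28 days while phase II cycles are not.
- *Short spacing will be common.* No figure in the documents says how often early starts would be used, and they require a judgement of best interest. The same rules also permit 35-day cycles and longer delays, so average intensity could fall below nominal.
- *Patients will exceed the maximum.* That requires dose level 0 to become the MTD.
- *It is unclear whether lirilumab moves with an early cycle.* Sections 5.2.1 and 5.3.3 say that it does.
- *Shorter spacing is shown to be harmful, or goes unmonitored.* Neither is so. Section 11.2 monitors drug-related grade 3/4 toxicity every 5 patients at whatever spacing was given, and Sections 5.3.2 to 5.3.4 set delay and discontinuation criteria. Section 2.4 reports no DLTs in dose escalation as monotherapy up to 10 mg/kg every 4 weeks (10/4 = 2.5 mg/kg/week), and describes a 3-weekly schedule with ipilimumab.

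That reassurance is partial. The 6 and 10 mg/kg monotherapy groups had 3 subjects each. The ipilimumab study had 18 subjects, 1 of them at lirilumab 3 mg/kg. None received this combination at this spacing. The toxicity rule pools all intervals, and by Table 6 the chance of stopping early is 0.4741 at a true toxicity rate of 0.40 and a true ORR of 0.30.

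**Conclusion.** The inconsistency is real and worth correcting. As written, the plan permits lirilumab 20-21 days apart with day-8 dosing, and 16-17 days apart in isolated intervals, against a stated maximum of every 4 weeks. The practical size is 1.33 times the stated maximum intensity under sustained 21-day cycles (1.00 against 0.75 mg/kg/week), on condition that dose level 0 becomes the MTD. The 1.65 and 1.75 ratios describe single intervals only, and 16 days further requires reading day 21 as the new day 1.

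The conclusion rests on the visible text. Section 6.1 refers lirilumab administration details to Appendix I, which is not reproduced; a minimum interval stated there would need to be carried into Section 5.2. The documents do not establish that shorter spacing is unsafe or that it would be frequent, and this point does not claim either.

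**What to change.** 1. Reconcile the every-4-weeks maximum in Sections 2.4 and 5.2.1 with the windows in Sections 3.0, 5.2.1, 5.2.2, 5.2.2.1 and 5.2.2.4. The sponsor should either state a minimum number of days from one lirilumab dose to the next, or correct the stated maximum so that it matches the permitted windows. Which interval is right is the sponsor's decision.
2. Reconcile the two wordings of the earliest restart: no sooner than day 21 (Section 5.2.2.1) and no sooner than 21 days after the prior cycle (Section 5.2.2.4). They differ by one day.
3. Add to Section 11.2 a tabulation of phase II toxicity by the lirilumab interval actually received. It needs only dosing dates.

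The cost is a few sentences by amendment and one extra table. The downside is small: with a minimum interval, the two drugs may fall out of step in some early-started cycles; with a corrected maximum, the stated ceiling looks less favourable.
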